8.1. Visit Schedule and Data Collection

The visit and data collection schedule is outlined in **Figure 3** below.

Figure 3 – Visit and Data Collection Schedule

Procedure/Assessment	Screening, Enrollment, Baseline	Procedure	30 Day Follow -up Visit (\pm 5 days)	Long Term Clinical Follow-Up Chart Review (Up to 24 months from Procedure)
ICF	X			
Eligibility Criteria Assessment	X			
Demographics	X			
Medical History	X			X
Lesion Location	X			X
Randomization	X			
Lesion Characteristics		X		X
EUS-FNA Procedure Details (including Needle Use and Times)		X		
Aspirate Characteristics		X		
Salvage EUS-FNA Procedure (if applicable)		X		
Adverse Events Assessment		X	X	
Additional Fluid Testing Results (if applicable)				X
Surgical Pathology (if applicable)				X

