8.6. Long Term Clinical Follow-Up Chart Review

After completion of the 30-day Follow-up Visit, a retrospective Long Term Clinical Follow-Up Chart Review will be performed to collect up to 24 months of standard of care clinical information (if applicable). There are no office or telephone visits required. The Investigator or study coordinator will review the hospital charts to assess patient status and extract PCL characteristic pertaining to Morphological Status, Cytopathological Status, Biochemical Status, and Surgical Pathology. No new Adverse Event information will be captured after the 30 Day Post Procedure.

9. Statistical Considerations

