Pseudocyst	Pigmented histiocytes	< 200

* This cytological assay might be replaced by another cytological assay as needed

In order to assess the accuracy of EUS-FNA-based standard assays (cytology and CEA) as a diagnostic measure of disease state, the *Disease State per EUS-FNA* measure will be compared to a reference diagnosis. The reference diagnostic standard will be diagnosis from a surgical specimen histology, the true gold standard for cases that evolve to surgical resection within the 30 day follow-up time of the protocol. For cases that do not progress to surgery within 30 days of the EUS-FNA procedure, the reference diagnostic standard will be a composite diagnosis by a consensus board. The consensus board will consist of 3 to 5 Investigators who will be blinded to the type of needle used. The diagnosis of disease state

will be based solely on baseline medical history and EUS and cross sectional imaging of the cyst. Information regarding aspirate characteristics and results from aspirate tests will not be provided to the consensus board. Diagnoses will be rendered at a separate Investigators Meeting or virtual meeting.

- “*Disease State per Histology*”: This is the reference diagnostic standard. This measure is derived from the histology results of the surgical specimen in cases that progress to surgery within 30 days. Cysts will be classified as follows: *serous cyst*, *mucinous cyst*, *IPMN*, *pseudocyst*, or *Indeterminate*. As described above, this measure will serve as the gold standard for assessing diagnostic accuracy.
- “*Disease State per Consensus Board*”: This is the surrogate for the reference diagnostic standard. This measure is derived by the consensus board as described above. Cysts will be classified as follows: *serous cyst*, *mucinous cyst*, *IPMN*, *pseudocyst*, or *Indeterminate*. The classification will be based on baseline medical history and EUS and cross sectional imaging. Medical history will include, but not be limited to presence or absence of prior necrotizing pancreatitis, trauma or other potential cause of pseudocyst. Imaging will pertain to cyst location and cyst appearance.

Degree of correlation between *Disease State per EUS-FNA* and *Disease State per Consensus Board or per Histology* is illustrated below.

Total number of patients enrolled is sum of all entries, namely

$$\text{TOTAL} = A + B + C + \dots + S + T + U + V + W + X + Y.$$

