#### 5.1.2 Diagnostic Accuracy Measures

Diagnostic accuracy is defined in terms of “disease state” and the following three disease state categories will be used in this study in order to assess diagnostic accuracy of EUS-FNA:

- “*Disease State per EUS-FNA*”: This measure is derived from the results of the cytology and chemistry assays of the cyst aspirate. Cysts will be classified as *serous cyst, mucinous cyst, IPMN, or pseudocyst* based on the table below. If any of the aspirate assays are not performed or the results from the two aspirate-based assays do not follow the table below, then the Disease State per EUS-FNA will be classified as

*Indeterminate.* The Disease State per EUS-FNA will be recorded on the *Cytology and Chemistry Results CRF*.

Disease State per EUS-FNA	Cytology	Cyst Fluid CEA (ng/mL)
Serous	Bland PAS +*	< 0.5
Mucinous	Mucinous	> 200
IPMN	Mucinous	> 200
Pseudocyst	Pigmented histiocytes	< 200

\* This cytological assay might be replaced by another cytological assay as needed

In order to assess the accuracy of EUS-FNA-based standard assays (cytology and CEA) as a diagnostic measure of disease state, the *Disease State per EUS-FNA* measure will be compared to a reference diagnosis. The reference diagnostic standard will be diagnosis from a surgical specimen histology, the true gold standard for cases that evolve to surgical resection within the 30 day follow-up time of the protocol. For cases that do not progress to surgery within 30 days of the EUS-FNA procedure, the reference diagnostic standard will be a composite diagnosis by a consensus board. The consensus board will consist of 3 to 5 Investigators who will be blinded to the type of needle used. The diagnosis of disease state will be based solely on baseline medical history and EUS and cross sectional imaging of the cyst. Information regarding aspirate characteristics and results from aspirate tests will not be provided to the consensus board. Diagnoses will be rendered at a separate Investigators Meeting or virtual meeting.

- “*Disease State per Histology*”: This is the reference diagnostic standard. This measure is derived from the histology results of the surgical specimen in cases that progress to surgery within 30 days. Cysts will be classified as follows: *serous cyst*, *mucinous cyst*, *IPMN*, *pseudocyst*, or *Indeterminate*. As described above, this measure will serve as the gold standard for assessing diagnostic accuracy.

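### Histology serves as the diagnostic reference only for surgery within 30 days, although surgical pathology is collected for up to 24 months; later-resected patients are scored against a history-and-imaging board

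*Protocol*

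**What the plan says.** Protocol Appendix C.3 and SAP 5.1.2 set the same reference for judging the disease state per EUS-FNA (secondary endpoint h). Surgical histology is described as "the true gold standard for cases that evolve to surgical resection within the 30 day follow-up time of the protocol". The definition of the histology measure repeats the limit: "This measure is derived from the histology results of the surgical specimen in cases that progress to surgery within 30 days".

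The rule for the remaining patients is: "For cases that do not progress to surgery within 30 days of the EUS-FNA procedure, the reference diagnostic standard will be a composite diagnosis", given by a consensus board of 3 to 5 investigators who are blinded to needle type. The board's diagnosis "will be based solely on baseline medical history and EUS and cross sectional imaging of the cyst", and aspirate results are withheld from it. On the standing of that diagnosis, C.3 says: "This is the surrogate for the reference diagnostic standard".

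Protocol 8.6 then provides that, after the 30-day visit, "a retrospective Long Term Clinical Follow-Up Chart Review will be performed to collect up to 24 months of standard of care clinical information", where applicable. The reviewer of the charts is to "extract PCL characteristic pertaining to Morphological Status, Cytopathological Status, Biochemical Status, and Surgical Pathology". Figure 3 in Protocol 8.1 marks surgical pathology only in the chart-review column, which runs up to 24 months from the procedure.

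The follow-up schedule in SAP section 1 ends at the 30-day visit and omits the chart review, which the protocol synopsis lists. Neither document brings histology obtained after day 30 into the reference diagnosis, the five-by-five table or a sensitivity analysis.

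**The concern.** The plan ranks histology above the board, yet sets histology aside when surgery falls after day 30. A patient resected on day 45 would have a histological diagnosis in the study database and still be scored against the board, even where the two disagree. The only basis given for the cut-off is the length of the protocol's follow-up, which is also the adverse-event window.

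Two things are at stake. First, an error by the board is counted as an error of the needle's assay result, or as a false agreement with it. Second, the histology-referenced and board-referenced groups do not overlap under the present rule. Later-resected patients are the only ones who would have both diagnoses, and no comparison of the two is planned, so the trial cannot say how often its surrogate is wrong. Accuracy for mucinous versus non-mucinous cysts is a named part of the primary objective.

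**Working it through.** The plan has no figure to reproduce here: endpoint h has no hypothesis, sample size or precision target. The check compares the time windows and then illustrates the size.

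**Windows.** Histology counts for 30 days; pathology is collected for up to 24 months, about 730 days. 30/730 is about 4% of the collection period.

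**Patients concerned (assumed).** If 5-15% of the planned 250 are resected between day 31 and month 24, that is 12.5 to 37.5, or about 12 to 38 patients. Under 2:1:1 allocation, one quarter falls in each standard-needle arm: 12.5/4 = 3.1 to 37.5/4 = 9.4, or about 3 to 9.

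**Effect of an imperfect board (assumed).** Take a binary mucinous/non-mucinous call, true accuracy *a*, and board error *e* independent of FNA error. Accuracy measured against the board is a(1−e) + (1−a)e. With e = 20%:
- a = 90%: 0.9×0.8 + 0.1×0.2 = 74%
- a = 80%: 0.8×0.8 + 0.2×0.2 = 68%

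A true 10-point difference appears as 6, a factor of 1−2e. This applies to board-scored patients.

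**What the change recovers.** If a fraction *f* of patients moves from board to histology, the factor becomes (1−f)(1−2e) + f. At e = 20%, f = 5% gives 0.95×0.6 + 0.05 = 0.62, and f = 15% gives 0.85×0.6 + 0.15 = 0.66.

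| Board error | All board-scored | f = 5% | f = 15% | Gain (points) |
|---|---|---|---|---|
| 10% | 8.0 | 8.1 | 8.3 | 0.1 to 0.3 |
| 20% | 6.0 | 6.2 | 6.6 | 0.2 to 0.6 |
| 30% | 4.0 | 4.3 | 4.9 | 0.3 to 0.9 |

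The gain is 10 × 2ef points. It does not depend on how many patients already have histology within 30 days, because they contribute equally before and after. It assumes the same *f* in each arm, and the same accuracies in later-resected patients as in the rest.

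**Estimating board error.** With board and histology both available in 12 to 38 patients, an error rate of 20% would have a 95% half-width of 1.96×√(0.2×0.8/12) = 23 points to 1.96×√(0.2×0.8/38) = 13 points. That is coarse, but the present rule provides no estimate at all.

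**The case against.** The case for leaving the rule alone has several parts.

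- A fixed window limits change in the lesion between aspiration and reference. This is a fair argument, but the documents do not make it. The reference categories are cyst types, not grades, so progression in grade alone would not move a patient between them.
- Later pathology comes from standard-of-care charts where applicable, so it is not collected systematically. The decision to operate may also depend on the aspirate result. Both points stand: a longer window brings in a selected group, so results should be reported by reference type.
- Endpoint h is secondary and, under SAP 5.1.1, summarised descriptively. No planned test of accuracy between needles loses power. This stands.
- Patients exit at 30 days and the final analysis follows study completion, so a 24-month reference could delay endpoint h or split it from the main report. This stands as a cost.

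Some stronger readings are tempting but not supported. A reader might infer that the 30-day limit costs the whole fall from 10 points to 6. That fall arises from having a board at all, and most of it remains because most patients will have no histology. A reader might call the board imaging-only, but it also uses baseline medical history. A reader might say the later pathology goes entirely unused. SAP 5.6.2 could cover it in a general descriptive summary, so the supportable statement is that it is not used as the reference.

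**Conclusion.** The point holds in a limited form. Both documents restrict their own gold standard to 30 days, pathology is scheduled for collection up to 24 months, and nothing connects the two. The consequence is confined to endpoint h and the diagnostic-accuracy part of the primary objective. The primary endpoint, endpoint c and the sample size are unaffected.

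Under the assumed ranges (5-15% later resection, 10-30% board error, independent errors), the change would make a true 10-point difference appear about 0.1 to 0.9 points larger. The documents supply neither rate, and the binary formula simplifies a five-by-five table with Indeterminate categories. It would also be wrong to conclude that board error must understate accuracy: correlated board and FNA errors could change the size or the direction of the bias. The benefit is therefore a better reference for some patients and a first, imprecise look at board error. This is a cheap improvement rather than the repair of a serious flaw.

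**What to change.** In Protocol C.3 and SAP 5.1.2:

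1. Define the histology reference as surgical histology from any resection recorded up to 24 months after FNA, and use the board diagnosis only where no histology exists.
2. Keep the 30-day rule as a prespecified sensitivity analysis. The board should therefore still review every case not resected within 30 days, on the same baseline information as now.
3. Report accuracy separately by reference type: histology within 30 days, later histology, and board.
4. Tabulate board diagnosis against later histology where both exist.
5. Add the chart review to the SAP follow-up schedule.

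If the sponsor prefers to keep the 30-day rule as the main analysis, it should state why and prespecify the later histology as a sensitivity analysis.

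The cost is mainly wording, since the data are already scheduled and patient management does not change. The downsides are that endpoint h is finalised only after the chart review, later resections are a selected group whose surgery may depend on the aspirate result, and some lesions may have changed by the time of surgery. Items 2 and 3 make the last two visible to the reader.

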## Revision History

Revision Number	Section	Change	Reason for Change

## 1 PROTOCOL SUMMARY

[figure not shown]
Primary Objective	To document impact of EUS-FNA needle gauge and flexibility on effectiveness of pancreatic cystic lesions (PCL) aspiration, on ability to obtain sufficient material for standard diagnostic testing, and on diagnostic accuracy of EUS-FNA aspirate for differentiation of mucinous (pre-malignant) and non-mucinous cysts.
Devices	
Name Expect™ Endoscopic Ultrasound Aspiration Needle
 
Cleared Indication The Expect™ Needle is designed to sample targeted sub mucosal and extramural gastrointestinal lesions through the accessory channel of a curvilinear echoendoscope.
 
Device Categories
 
 
• Expect 22 gauge (22 G)
 
• Expect 19 gauge (19 G)
 
• Expect 19 gauge Flex (19 G Flex)
 

Study Design	
Prospective, multi-center study
 
Three arm randomized (19 G Flex, 22 G, 19 G) in 2:1:1 ratio with salvage. Salvage procedure will use 19 G Flex for subjects originally randomized to 19 G or 22 G standard needles, and will use 19 G or 22 G standard needle at investigator discretion for subjects originally randomized to 19 G Flex needle.
 
Phased
 
 
• Phase I: 2 centers
 
• Phase II: expanded to 7 to 12 centers
 

Number of Subjects	250 subjects (121 in 19 G Flex arm, and 61 subjects each in 22 G and 19G arm, rounded up) 30 out of the 250 subjects will be enrolled in Phase I, and 220 subjects will be enrolled in Phase II.
Number of Centers	7 to 12 centers
Primary Endpoint	Volume of aspirated cyst fluid as a function of estimated maximal volume based on pre-aspiration EUS measure of cyst diameter (s) (%)

	aspiration of total estimated volume)
Secondary Endpoints	
Safety Endpoint
 
a. Occurrence, severity and relatedness of adverse events to the needle and procedure
 
Other Endpoints
 
b. Extent of cyst aspiration as measured by reduction of maximal cyst diameter before and after FNA (converted to volume by standard geometric formulation)
 
c. Successful echoendoscopic fine needle aspiration of PCL, defined as complete cyst aspiration or collection of aspirate adequate to perform two standard assays: cytology and carcinoembryonic antigen (CEA)
 
d. Ability to reach and penetrate the PCL, stratified by route of access and PCL location
 
e. Number of EUS-FNA needles and EUS-FNA needle passes used
 
f. Time needed for aspiration for each pass and time from first needle pass in to last needle pass out
 
g. Ease of needle passage in and out of echoendoscope and quality of needle visualization inside the cyst, categorized as Excellent, Very Good, Good, Fair, and Poor
 
h. Accuracy of two EUS-FNA-based standard assays (cytology and CEA) as a diagnostic measure of disease state categorized as one of the following: serous cyst, mucinous cyst, intra papillary mucinous neoplasm (IPMN), or pseudocyst
 
i. Post EUS-FNA patient management plan (clinical and/or imaging surveillance, percutaneous aspiration, surgical removal)
 
j. Impact of EUS-FNA based assays on diagnosis
 
k. Rate of cross-over to salvage arm

Follow-up Schedule	
 
• Baseline: Screening, Enrollment, Randomization, Demographics, Medical History, Lesion Location
 
• Procedure: Lesion Characteristics, EUS-FNA Procedure Details (including needle use and times), Aspirate Characteristics, Salvage Procedure (if needed), Adverse Events assessment (through discharge or approximately 2hrs post-procedure)
 
• 30-Day Follow-up: Adverse events, End of Study
 

Inclusion	1. Pancreatic cystic lesion measuring 13mm or greater in largest

Criteria	
diameter.
 
 
2. Indicated for EUS evaluation of the PCL including EUS-FNA.
 
3. Age 18 years of age or older.
 
4. Willing and able to comply with the study procedures and provide written informed consent form to participate in the study.
 

Exclusion Criteria	
 
1. Cysts in which FNA is not indicated based on review by the clinician, including potential concern of blood vessel location relative to the cyst.
 
2. Requirement for anticoagulation using clopidogril, warfarin, or other long acting antiplatelet agents (with the exception of aspirin) that cannot be safely stopped according to institutional guidelines.
 
3. Standard contraindications for EUS.
 
4. Known pancreatic pseudocyst.
 
5. Pregnancy.
 

Statistical Methods and Sample Size	
The sample size of this study was computed based on the following assumptions on the primary endpoint, as well as for the secondary endpoint c):
 
Primary endpoint considerations:
 
 
• The volume of actual aspirated cyst fluid as a function of estimated maximal volume either in 19 G or 19 G Flex Arm is superior by at least 10% compared to the 22 G Arm, detected with 90% conjunctive power, using multiple comparison Hochberg's step up method.
 
• Requires 50 subjects in 19 G Flex Arm, and 25 subjects each in 22 G and 19 G Arms.
 
 
Secondary endpoint c) considerations:
 
 
• Superiority of EUS-FNA success rate in 19 G Flex Arm by 16% or more compared to both the success rate of the 19 G Arm and the 22 G Arm, detected with 80% conjunctive power, using multiple comparison Hochberg's step up method.
 
• Requires 121 subjects in 19 G Flex Arm, and 61 subjects each in 22 G and 19G Arm, rounded up
 
 
The final sample size was considered to be the maximum of required sample sizes of the above stated two endpoints to make sure that the both endpoints are properly powered, namely 250 subjects.

A flow chart illustrating the study design is provided in **Figure 1** below.

**Figure 1 – Study Design Flow Chart**

## 2 INTRODUCTION

This statistical plan addresses the planned analyses for the Randomized Evaluation of PCLs Using Three EUS-FNA Needles Trial based on the protocol with PDM 90869947. Specified analyses may be used for scientific presentations and/or manuscripts and may not all be provided to Competent Authorities.

### 3 ENDPOINT ANALYSIS

#### 3.1 Primary Endpoint

##### 3.1.1 Hypotheses

The primary endpoint is “Volume of aspirated cyst fluid as a function of estimated maximal volume based on pre-aspiration EUS measure of cyst diameter (s) (% aspiration of total estimated volume).”

Analysis Approach:

% aspiration of total estimated volume is calculated overall and for each arm (19 G Flex, 22 G, 19 G) and/or a combination of arms such as 19G Flex and 19G, for each and combined morphologic characteristics, and for no salvage subjects. If there is multilocular morphology, the primary endpoint is calculated for measurements of the largest locule.

Valid Data Sources:

- Procedure Form: sections “PCL Characteristics” and “Post-Aspiration Assessment”

Valid Data Points:

- Morphology: Unilocular (Pre-aspiration EUS measures)
  - Maximal diameter (long axis) (mm)
  - Perpendicular measurement (short axis) (mm)
- Morphology: Multilocular (Pre-aspiration EUS measures)
  - Measurements of the largest locule
    - Maximal diameter (long axis) of the largest locule (mm)
    - Perpendicular measurement (short axis) of largest locule (mm)
- Total volume of aspirate (Post-aspiration assessment)

Formula:

$$\% \text{ aspiration of total estimated volume} = \frac{A-B}{A} \times 100 \%$$

Volume is computed using the standard geometric formula  $\left(\frac{4}{3}\pi R^3\right)$  where R is half the long axis. The volume unit is in cc. “A” is calculated by the image during pre-procedure measurements. “B” is calculated by the image during post-procedure measurements.

Hypotheses:

$H_{0i}: \mu_i - \mu_0 \leq 0$  Versus  $H_{1i}: \mu_i - \mu_0 > 0$  for  $i=1, 2$ ;

where  $\mu_0$  is mean volume percentage of 22 G Arm,  
 $\mu_1$  is mean volume percentage of 19 G Flex Arm, and  
 $\mu_2$  is mean volume percentage of 19 G Arm.

Superiority by 10% or more is deemed clinically significant.

The multiple comparison Hochberg's step up method will be used.

The analysis population for the primary endpoint will be the Intent to Treat and Per-protocol analysis sets.

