4.1. Primary Endpoint

Volume of aspirated cyst fluid as a function of estimated maximal volume based on pre-aspiration EUS measure of cyst diameter (s) (% aspiration of total estimated volume).

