7.2. Needle Puncture and Aspirate Requirements

The following procedural rules will be followed:

- a. Initial needle puncture with stylet in place (with time stamp). Remove stylet and apply 10cc suction. If no aspirate visible in syringe lumen after 5 seconds of suction: reposition needle and re-apply suction. If no aspirate after 5 seconds of suction- lesion classified as FNA failure. Switch to salvage method.

- b. If aspirate visible within syringe lumen, hold suction until no additional material accumulated for 10 seconds. If cyst completely collapses, note final time stamp. If cyst is not completely collapsed, then repositioning is allowed until all cyst locules have been punctured, and no additional fluid is obtained for 10 seconds. Note final time stamp. If cysts is not completely collapsed after attempts, above, note final maximal and perpendicular diameter.
- c. In case of a multi-compartment, loculated lesion, all locules accessible with the same needle pass will be aspirated, with priority to the largest locule. In cases where a locule is positioned in front of another along the axis of the needle, the one most proximal to the needle tip should be fully aspirated before accessing the locules located in a more distal position.
- d. In the event that cyst components cannot be reached without repuncture, remove needle completely from cyst (note time stamp for pass completion). Repuncture for pass 2 (or more) as needed until criteria (see "b" above) for complete aspiration or failure is met.
- e. If maximal cyst diameter is > 5mm after efforts described in "b" above, cyst aspiration is considered "failed." Switch to salvage method (19 Flex, if first method was not 19 Flex).

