7.4. Post-Procedure Handling of Cyst Aspirate

- a. Record final cyst maximum diameter and perpendicular diameter.
- b. Record total volume of cyst aspiration by suctioning all material, including what is in the needle lumen, into the syringe, inverting it, and removing air.
 - If sample volume is > 3cc, send 2cc to chemistry laboratory for CEA. Send remainder to cytology lab.
 - If sample volume is < 3cc, divide the sample into two aliquots guided by volumetric requirements of the local cytology and chemistry labs.
 - Sequential portions of the aspirate will be used for the two assays as follows:
 - o First aliquot (preferably at least 1cc) – Cytology
 - o Second aliquot (preferably at least 1cc) – CEA
 - o All remaining fluid is to be added to the first aliquot and sent for cytology

- In case the total aspirate volume is insufficient to satisfy local cytology and chemistry lab requirements, then the aliquot order outlined above should be used to prioritize which subset of assays will be performed.
- In cases in which the aspirate volume is more than 1 cc but less than 3 cc, the first cc should be sent for cytology and the remainder should be sent for CEA. Some laboratories may have the ability to perform CEA assays on less than 1 cc of fluid for assay.
- In cases in which the aspirate volume is less than 1 cc, the aspirate will nevertheless be sent for cytology.

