8.3. Procedure

8.3.1. Lesion Characteristics

The following lesion characteristics will be assessed by EUS prior to the start of the FNA procedure and will be recorded on the *Procedure CRF*:

- a. Cyst size (maximal diameter, and cross-sectional diameter)

NOTE: In the case of a multilocular cyst, size will be measured both as the aggregate size of all cyst locules and the long and short perpendicular axis of the largest locule.

- b. Number of locules (1, 2, 3, 4, 5, 6-10, > 10)
- c. Presence of visible mucin (floating, or mobile filling defects)
- d. Presence of mural nodule (non-mobile filling defect) and size
- e. Presence of solid components
- f. Presence of distinct PCL wall
- g. Connectivity to pancreatic duct
- h. Maximal pancreatic duct diameter

An EUS image of the patient's PCL will be saved during the procedure.

8.3.2. *EUS-FNA Procedure*

The EUS-FNA procedure will be carried out in line with the guidelines provided in **Section 7** above, and the following data will be collected and recorded on the *Procedure CRF*:

- a. Route of access (gastric, duodenal, esophageal)
- b. Ease of insertion of EUS-FNA needle through echoendoscope
- c. Ability to reach target lesion
- d. Ability to penetrate into target lesion
- e. Quality of needle visualization
- f. Number of needle passes
- g. Ease of removal of EUS-FNA needle from echoendoscope
- h. Aspirate characteristics and adequacy of aspirate volume to perform two assays (cytology and CEA)
- i. Adverse Event assessment during procedure and through 2 Hours Post-Procedure or discharge from endoscopy unit

8.4. **Cytology and Chemistry Results**

The results of cyst aspirate cytology and CEA assessments will be provided by the cytology and chemistry labs and will be recorded on the *Cytology and Chemistry Results CRF*. Results will be categorized as follows⁴ and will be used for determination of Disease State per EUS-FNA:

- Cytology
 - Bland PAS +
 - Mucinous
 - Pigmented histiocytes
- CEA (ng/mL)
 - < 0.5
 - > 0.5 and < 200
 - > 200

8.5. **30-Day Follow-up**

The post-procedure 30-day Follow-up Visit will be conducted over the telephone. The visit window allows for this visit to occur anytime from 25 days to 35 days post procedure. Patients will be assessed for potential adverse events that might have occurred from discharge until 30 days post-procedure. AE information will be recorded on the *Adverse Event CRF*.

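### The primary percentage in SAP 3.1.1 uses the long axis only and, in multilocular cysts, the largest locule only, so it can misstate how much of the cyst was emptied

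*SAP*

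**What the plan says.** Protocol 4.1 defines the primary endpoint as "Volume of aspirated cyst fluid as a function of estimated maximal volume", expressed as a percentage of the total estimated volume.

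SAP 3.1.1 turns this into (A-B)/A x 100%. A and B are image volumes before and after the procedure, each taken as 4/3 x pi x R^3, "where R is half the long axis". For cysts with several locules, "If there is multilocular morphology, the primary endpoint is calculated for measurements of the largest locule". The same section lists "Perpendicular measurement (short axis) of largest locule (mm") as a valid data point, and likewise the short axis of a unilocular cyst. Neither is used in the formula. The list contains no post-aspiration diameter, although B needs one.

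The protocol has more fluid removed, and more measured, than the formula uses:

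- Section 7.2, item c: "all locules accessible with the same needle pass will be aspirated, with priority to the largest locule".
- Section 8.3.1, multilocular cysts before aspiration: "size will be measured both as the aggregate size of all cyst locules and the long and short perpendicular axis of the largest locule".
- Section 7.4, item a, after aspiration: "Record final cyst maximum diameter and perpendicular diameter". For a multilocular cyst it does not say whether this means the whole lesion or one locule.

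Neither document gives a reason for the sphere or for scoring one locule, and neither plans a sensitivity analysis with the short axis or the aggregate size.

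**The concern.** The endpoint is meant to say what share of the cyst was emptied. Two features of the formula can separate the reported figure from that share.

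**Shape.** A cyst that loses fluid may flatten, so that its short axis falls by proportionally more than its long axis. A volume built on the long axis alone misses part of that loss.

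**Compartment.** In a multilocular cyst the formula describes one locule, while the endpoint speaks of the total volume and the procedure covers every accessible locule. It is also unclear whether the final measurement (B) is taken on the same structure as A.

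Locules matter on the plan's own evidence. In Protocol 9.1.1, Figure 4, one investigator expected 90% for unilocular and 50% for multilocular cysts with the 19 G needles, a gap of 40 points. At stake are the meaning of the reported percentage and of the 10-point difference called clinically significant, and some avoidable patient-to-patient noise. A bias between needles would need the needles to differ in collapse pattern or in reach into the other locules.

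**Working it through.** **The plan's own figure.** SAP 3.1.2 states conjunctive power 0.901 and global power 0.912 for means 67/77/77, SDs 15.29/4.67/4.67 and n = 25/25/50 (22 G, 19 G, 19 G Flex), at one-sided alpha 0.05 with Hochberg. Simulation with 400,000 runs gives 0.904 and 0.915 with Welch t-tests, and 0.915 and 0.927 with the normal reference of SAP 3.1.3. The stated figures reproduce. The means and SDs derive from investigators' estimates of the percentage, so the geometry below does not alter them.

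**Inputs for the geometry.** The formula is from SAP 3.1.1. The documents give no distribution of cyst dimensions, so all dimensions below are illustrative assumptions. L and S are the long and short axes. The third axis is not recorded; taking it as S or as L gives a range.

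- Sphere (SAP): V = pi/6 x L^3
- Ellipsoid, third axis S: V = pi/6 x L x S^2
- Ellipsoid, third axis L: V = pi/6 x L^2 x S

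**Step 1: shape, unilocular cyst of 30x20 mm.** The factor pi/6 cancels in (A-B)/A.

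| Residual (mm) | Sphere | L x S x S | L x L x S |
|---|---|---|---|
| 15x10 | 1 - 15^3/30^3 = 87.5% | 87.5% | 87.5% |
| 20x5 | 1 - 20^3/30^3 = 70.4% | 1 - 500/12000 = 95.8% | 1 - 2000/18000 = 88.9% |
| 25x5 | 1 - 25^3/30^3 = 42.1% | 1 - 625/12000 = 94.8% | 1 - 3125/18000 = 82.6% |

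The first row has the same S/L before and after (0.667), and the error cancels. In the second, S/L falls from 0.667 to 0.25. Relative to L x S x S, the sphere then overstates the residual share by (0.667/0.25)^2 = 7.1: 29.6% instead of 4.2%.

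**Step 2: multilocular cyst, spherical locules of 20, 15 and 15 mm.** Volumes are 4.19 + 1.77 + 1.77 = 7.72 cc (rounded).

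- Only the largest emptied: SAP score 100%; share of the cyst emptied 4.19/7.72 = 54%.
- Largest reduced to 10 mm, the others emptied: SAP score 1 - (10/20)^3 = 87.5%; share emptied 1 - 10^3/(20^3 + 2 x 15^3) = 93%.

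The error can go either way.

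**Step 3: compartment of B.** Take a 20 mm largest locule, fully emptied, with A measured on it.

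- B on the same locule: 100%.
- B on a remaining 18 mm locule: 1 - (18/20)^3 = 27%.
- B on a residual lesion of 25 mm overall: 1 - (25/20)^3 = -95%.

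The SAP has no rule for values outside 0 to 100%.

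**The case against.** **The largest locule is a consistent target.** Eligibility (Protocol 5.2), aspiration priority (7.2) and complete aspiration under endpoint c (4.2) all rest on it, and the SAP sentence most naturally covers B as well as A. This stands in part. The 27% and -95% results are possible readings, not what the SAP prescribes, and the Procedure Form that might settle the matter is not in the documents. But those other uses are thresholds or priorities, not a percentage of the total volume, so the 100%-against-54% example remains even on the natural reading.

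**The ellipsoid is also an assumption.** True: the third axis is unmeasured, hence 89% to 96% and not one value. In the flattening examples both versions lie well above the sphere.

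**Part of the remedy is already planned.** SAP 3.1.1 has results by morphology, and SAP 5.5 relates the primary endpoint to PCL size and number of locules. This stands. What is missing is a stated role for the unilocular result.

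**Stronger readings a reader might infer.** One is that the percentage can exceed 100%, or that a fully emptied elongated cyst scores well under 100%. The SAP formula does neither: B cannot be negative, and B = 0 gives 100% for any shape. Such values need the protocol's ratio of aspirate to A: 184% if all three locules of Step 2 are emptied (7.72/4.19), and 44% to 67% for an emptied 30x20 mm cyst (6.28 or 9.42 cc against 14.14 cc). Another is that a 10-point margin is tested on the wrong scale. SAP 3.1.1 tests a difference of zero or less; 10 points is the planning effect, and the investigators' estimates specify no geometry. A third is that the test is invalid. Randomisation (Protocol 8.2.4) balances shape and locule number in expectation, so type I error is not threatened.

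**Conclusion.** The point holds in a limited form. Applied exactly as written, SAP 3.1.1 understates emptying when a cyst flattens (70% against 89% to 96% in the example). It scores one locule where the endpoint refers to the total volume (100% against 54%). It also leaves open which compartment B describes, so a far too low or negative value is possible if B is not the largest locule. There is no error for a unilocular cyst that keeps its shape or is fully emptied.

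The sizes rest on illustrative dimensions; how often such cysts occur cannot be learned from the documents. The harm is to the meaning and precision of the percentage, not to the stated power or the type I error. This should be fixed because it is cheap, but it does not invalidate the plan. That the SAP formula contains no aspirated volume at all, contrary to Protocol 4.1, is a separate matter; it needs settling too, because the numerator determines which of these errors arise.

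**What to change.** Change SAP 3.1.1 before arm-level results are examined:

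1. **Both axes.** Compute A and B as pi/6 x long x short x short from the recorded axes. Keep the long-axis sphere as a sensitivity analysis. List the two post-aspiration diameters as valid data points.
2. **One compartment.** State that A and B (or the aspirate and A) refer to the same structure. Where B was measured on the whole cyst, or total aspirate is the numerator, use the recorded aggregate size for A. Otherwise label the result as emptying of the largest locule. State how values outside 0 to 100% are handled.
3. **Aggregate-size sensitivity analysis**, as far as the data allow. Protocol 8.3.1 records an aggregate size but names long and short axes only for the largest locule. If the aggregate is a single dimension, A and B must both use the one-axis formula in that analysis.
4. **Unilocular cysts.** Designate the already planned unilocular result as the supporting analysis.

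The cost is SAP wording and a derived variable; Protocol 7.4 and 8.3.1 already record the axes needed for item 1. The downsides are that the third axis is still assumed, and that aggregate size includes septa and unreachable locules, so multilocular percentages may look less favourable.
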